#### 5.2. Secondary Endpoints

The secondary endpoints are as follows:

- Positive predictive value (PPV) of the PillSense System
- Negative predictive value (NPV) of the PillSense System
- Transit of the PillSense Capsule through the GI tract (yes/no)

PPV and NPV are defined as follows:

## **STATISTICAL ANALYSIS PLAN**

PPV: Probability of patients who have a “Blood detected” result having bleeding.

True Positives

---

True Positives + False Positives

NPV: Probability of patients who have a “No Blood detected” result and have no bleeding.

True Negatives

---

True Negatives + False Negatives

The above secondary endpoints are descriptive and will not be evaluated with a hypothesis test, and therefore no adjustment for multiplicity is required.

### **5.3. Exploratory Analysis**

The exploratory analysis are as follows:

- Positive likelihood ratio (PLR) of the PillSense System
- Negative likelihood ratio(NLR) of the PillSense System
- Accuracy of PillSense capsule

These are defined as follows:

PLR: Probability (odds) of having “Blood detected” in a patient with bleeding.

Sensitivity

---

1-Specificity

NLR: Probability (odds) of having “Blood detected” in patients with no bleeding/

1-Sensitivity

---

Specificity

Accuracy: Correct classification rate is the proportion of observations for which the test result and actual response agree.

## STATISTICAL ANALYSIS PLAN

True positive + True negative

---

True positive + False negative + True negative + False positive

### 5.4. Safety Parameters

Safety will be assessed based on adverse events.

Summaries of adverse events (AEs) will be limited to treatment-emergent adverse events (TEAEs), which are those adverse events that begin or worsen after initiation of “treatment” with the investigational device (i.e., administration of the PillSense Capsule).

For AEs with a missing start date, the AE will be considered treatment-emergent unless there is additional information indicating that the AE started prior to study treatment.

The numbers and percentages of subjects with the below will be presented:

- at least one TEAE,
- at least one serious TEAE,
- at least one severe TEAE,
- at least one TEAE suspected to be related to the investigational device,
- at least one adverse device effect (ADE),
- at least one serious adverse device effect (SADE),
- at least one unanticipated serious adverse device effect (USADE), and any deaths.

AEs with a related, probable, or possible relationship, or for which the relationship is missing, will be considered related.

TEAEs and serious TEAEs will be summarized at the subject level by MedDRA system organ class (SOC) and preferred term (PT) using frequencies and percentages. TEAEs will also be summarized at the event level by SOC, PT, and severity and by SOC, PT, and relationship to the investigational device.

## **STATISTICAL ANALYSIS PLAN**

### **6. GENERAL STATISTICAL CONSIDERATIONS**

#### **6.1. General Descriptive Analysis**

Data collected in this study will be documented using summary tables and subject data listings. Continuous variables will be summarized using descriptive statistics, specifically the number of observations, mean, median, standard deviation, minimum and maximum. Categorical variables will be summarized using frequencies and percentages.

#### **6.2. Sample Size**

Calculations were performed to estimate the minimum total sample size (TSS) required to achieve at least 80% probability of observing a successful outcome for both sensitivity and specificity to detection of Upper GI Bleed (UGIB), each relative to a performance goal. These calculations were performed assuming a prevalence of UGIB (PR) of 30%.

The probability of meeting the sensitivity endpoint is independent from the probability of meeting the specificity endpoint because they are based on different groups of patients. Therefore, the probability of meeting both endpoints (P) was calculated by multiplying the probabilities of meeting the sensitivity and specificity endpoints individually (i.e., by multiplying the statistical powers for the two endpoints).

The power for sensitivity was calculated based on the following specifications:

1. Single-arm study of PillSense
2. Primary endpoint: sensitivity to detection of Upper GI Bleed (UGIB)
3. Comparison to Performance Goal
4. True sensitivity: 0.975
5. Performance Goal: 0.75
6. Z-test with continuity correction
7. One-sided alpha = 0.025
8. Prevalence of UGIB = 30%

The power for specificity was calculated based on the following specifications:

1. Single-arm study of PillSense
2. Primary endpoint: specificity to detection of Upper GI Bleed (UGIB)
3. Comparison to Performance Goal
4. True specificity: 0.80
5. Performance Goal: 0.60
6. Z-test with continuity correction
7. One-sided alpha = 0.025
8. Prevalence of UGIB = 30%

Based on the above specifications, it was determined that 86 subjects (26 with UGIB for sensitivity and 60 without UGIB for specificity) are the minimum TSS that achieves ~80% probability of meeting both the sensitivity and specificity endpoints. With respect to specificity, study enrolment will continue until at least 60 subjects without UGIB are observed. The sample size for specificity

## STATISTICAL ANALYSIS PLAN

may be increased to a maximum of 120 patients to ensure that at least 60 mITT patients without UGIB are detected if the observed prevalence of UGIB during the trial is different from that assumed (i.e., 30%).

#### 6.4. Analysis Population

a. modified Intent to Treat Population (mITT)

Will include all subjects with PillSense and EGD data. The primary and secondary endpoints will be analyzed based on the mITT Population. Any patients with missing primary endpoint data (either no PillSense Capsule reading or no EGD result) will be excluded from the primary and secondary endpoint analyses; however, we will report on the frequency and reason with which this occurs.

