### **7.3 Study Objectives**

The study objectives are the following:

- to demonstrate the PillSense System can detect blood in the stomach in clinically relevant scenarios and heterogeneous environment of the upper GI tract.
- to assess the sensitivity, specificity, positive predictive value (PPV), and negative predictive value (NPV) of the PillSense System in a clinical environment.
- to show that the PillSense Capsule will pass through the GI tract without incident in a timely manner.

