### 7.5.4 Recording procedures

The following procedures or documentation was to be obtained at the time of PillSense Capsule administration.

- The Investigator ensured that the Subject had been fasting at least 2 hours if intake of only clear liquids or 4 hours for PO intake other than clear liquids
- The Investigator paired the PillSense Capsule to its Receiver Unit in accordance with the Instructions for Use (see Appendix 16.4)
- The Investigator provided the PillSense Capsule to the Subject which was ingested with approximately 150mL of water
- The Subject was asked to lie on their left side on a bed
- The PillSense Receiver was placed next to the Subject
- The PillSense Receiver recording was initiated once the Subject was comfortable
- The PillSense Receiver was monitored, and the output recorded on the Case Report Form and a photograph taken of the monitor screen to document the result, i.e., "Blood detected" or "No blood detected"

Subjects that could not or refused to swallow the capsule were withdrawn. Reason for withdrawal was documented on the End of Study form.

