**b. Safety Population**

Will include all subjects who receive a PillSense capsule. Safety will be analyzed based on the Safety Population.

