#### **8.2. Statistical Methods for the Secondary Efficacy Endpoints**

Secondary analysis will be performed based on mITT population. Secondary endpoints are for informational purposes only.

- Observed value along with exact (Clopper Pearson) 95% CI of Positive Predictive Value (PPV)
- Observed value along with exact (Clopper Pearson) 95% CI of Negative Predictive Value (NPV)
- Observed value along with exact (Clopper Pearson) 95% CI of Positive Likelihood Ratio (PLR)
- Observed value along with exact (Clopper Pearson) 95% CI of Negative likelihood Ratio (NLR)
- Observed value along with exact (Clopper Pearson) 95% CI of Accuracy.

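### Capsule transit is analysed only in subjects with a reading and an EGD, and no visible rule says how never-confirmed passage is counted

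*SAP*

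**What the plan says.** Protocol 7.3 lists three objectives. One is "to show that the PillSense Capsule will pass through the GI tract without incident in a timely manner". SAP 5.2 turns it into a yes/no secondary endpoint, adding that "The above secondary endpoints are descriptive and will not be evaluated with a hypothesis test".

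On the analysis set, SAP 6.4 says "The primary and secondary endpoints will be analyzed based on the mITT Population". For anyone lacking an EGD or a capsule reading, the rule is that they "will be excluded from the primary and secondary endpoint analyses; however, we will report on the frequency and reason with which this occurs". SAP 8.2 repeats the choice: "Secondary analysis will be performed based on mITT population. Secondary endpoints are for informational purposes only". No exception is made for transit. SAP 8.2 lists an exact 95% interval for PPV, NPV, both likelihood ratios and accuracy, but transit is not on the list.

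The Safety Population is defined separately: "Will include all subjects who receive a PillSense capsule". It is assigned to the safety analysis only. Protocol 7.5.4 adds that "Subjects that could not or refused to swallow the capsule were withdrawn".

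On missing data, SAP 6.5 takes mITT subjects with missing values out of the percentage, reports how many there are, and assumes that missingness is random. SAP 9 derives time to passage from a passage date and is silent on capsules without one. Protocol 7.1, 7.5.6 and 7.5.7 provide for follow-up and X-ray where passage is unconfirmed. Protocol 7.4.3 provides an exit interview, as far as possible, for subjects who withdraw, and foresees loss to follow-up.

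**The concern.** A reading and an EGD are needed to judge diagnostic accuracy. They have no part in whether a swallowed capsule left the body. A subject whose capsule gave no reading, or who never had the EGD, can still pass or retain it, and the protocol follows all patients for that outcome. Under SAP 6.4 even a retained capsule shown on X-ray in such a subject would not enter the transit endpoint.

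The second gap is coding. A capsule seen on X-ray is a natural *no*. A capsule whose fate was never established is not classified anywhere visible: SAP 5.2, 6.4, 6.5, 8.2 and 9 are where a rule would be expected, and all are silent. The reported percentage then rests on a choice that could be made after the data are seen. No success decision depends on it, since transit has no performance goal and no test. What is at stake is the figure that answers a stated objective.

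**Working it through.** **Inputs.** The plan gives no transit rate, target, non-reading rate, no-EGD rate or loss rate, so there is no transit figure to reproduce and every count below is assumed. The 86 is the minimum sample size in SAP 2 and 6.2, used only as a convenient mITT denominator. Intervals are Clopper-Pearson 95%.

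**Step 1: coding effect within mITT.** With x confirmed passages, n subjects and m never confirmed, the rate is x/n if the m count as *no*, and x/(n−m) if they are dropped under SAP 6.5. The difference is x·m/[n(n−m)], which is positive whenever x and m are positive. With n = 86 and one retained capsule, x = 85 − m:

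| m | Dropped as missing | Counted as *no* | Gap (points) |
|---|---|---|---|
| 1 | 84/85 = 98.82% | 84/86 = 97.67% | 1.15 |
| 2 | 83/84 = 98.81% | 83/86 = 96.51% | 2.30 |
| 3 | 82/83 = 98.80% | 82/86 = 95.35% | 3.45 |
| 5 | 80/81 = 98.77% | 80/86 = 93.02% | 5.74 |

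For m = 3 the intervals are 93.5 to 100.0% (dropped) and 88.5 to 98.7% (*no*). As an outer case, 13 of 86 never confirmed (15%) and none retained gives 73/73 = 100% against 73/86 = 84.9%, a gap of 15.1 points. With no proven retention, the dropped version reads 100% whatever m is.

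**Step 2: comparison with the unknown truth.** If all three unconfirmed capsules in the m = 3 row had in fact passed, the true rate would be 85/86 = 98.84%, and the dropped version (98.80%) would be marginally too low. The direction in Step 1 is therefore relative to *no* coding only.

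**Step 3: population effect, like for like.** Take the m = 3 row (82 passed, 1 retained, 3 not confirmed) and add 4 subjects who swallowed the capsule but lack a reading or an EGD: 3 passed, 1 not confirmed. The Safety total is 90.

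- Unconfirmed dropped: mITT 82/83, Safety 85/86, both 98.8%.
- Unconfirmed as *no*: mITT 82/86 = 95.3%, Safety 85/90 = 94.4% (87.5 to 98.2%), a difference of 0.9 points.
- All 4 added subjects unconfirmed, as *no*: Safety 82/90 = 91.1% (83.2 to 96.1%).
- All 4 added subjects passed, with the three mITT unconfirmed still *no*: Safety 86/90 = 95.6%, slightly above mITT.

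The effect is small unless subjects without a reading or EGD are also those whose passage is unknown, such as early withdrawals. It has no fixed direction.

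**Step 4: bounds on the full denominator.** In the base example the worst case is 85/90 = 94.4% and the best case (85 + 4)/90 = 89/90 = 98.9% (94.0 to 100.0%). If the one unconfirmed added subject were instead known to have retained the capsule, the best case falls to 88/90 = 97.8%, while the mITT figure does not change at all. That is the loss of information caused by SAP 6.4.

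**Step 5: exclusions and the accuracy endpoints (minor).** The planned statistic is z = (x − n·p0 − 0.5)/√(n·p0·(1−p0)), compared with 1.960. The pass marks are 25/26 for sensitivity and 44/60 for specificity. At the design values they give 0.863 × 0.923 = 0.796, which agrees with the roughly 80% in SAP 6.2. At the specificity boundary, 44/60 passes: (44 − 36 − 0.5)/√14.4 = 1.98. With one non-reading counted as wrong, 44/61 gives (44 − 36.6 − 0.5)/√14.64 = 1.80, and the exact lower limit is 59.2%; both fail. At the expected 48/60, six such subjects are tolerated: 48/66 gives z = 1.985 and a lower limit of 60.4%. These are stress tests, not estimates of bias.

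**The case against.** The strongest case is that little turns on this. Transit is descriptive. SAP 6.5 reports the number missing, so a reader could rebuild 82/86 from 82/83. SAP 6.4 reports exclusions with reasons, and SAP 7.1 adds a flowchart. SAP 7.6 also summarises time to excretion without stating an mITT restriction. X-ray follow-up should settle most capsules, leaving mainly lost or withdrawn subjects.

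All of that stands and limits the weight of the point. It does not close it. Time to excretion needs a passage date, so it says nothing about capsules without one. The exclusion counts for missing readings or EGDs do not show whether those subjects passed the capsule.

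A reader might infer that the plan tilts transit in the device's favour. The documents do not support that: the uplift exists only against *no* coding (Step 2), and the missing coding is itself only one possible reading. Nor do they support a claim that using mITT inflates the rate (Step 3). It would also go too far to say that the plan contains no rule at all, since SAP 6.3 and the closing pages are redacted.

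**Conclusion.** The point holds in a limited form. mITT is the wrong denominator for transit because its entry conditions are unrelated to passage and can remove known retained capsules. The coding of never-confirmed passage is undefined in the visible text. The coding choice is worth about 1 to 6 points for 1 to 5 unconfirmed subjects among 86 with one retained; the population choice is worth 0.9 points or less in the base example. Both sizes rest on assumed counts, because the documents give no rates. The change is worth making because transit serves a stated objective, but no pass/fail result depends on it.

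A reader might extend this to the primary analysis and call it invalid. That does not follow. mITT is a reasonable primary set for sensitivity and specificity. The random-missingness assumption without a visible check is a gap in supporting analysis, and its importance cannot be sized from the documents.

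**What to change.** **Transit.** Analyse it on the Safety Population, limited to subjects who swallowed the capsule. Class each at study exit (Day 21 at the latest) as passed, retained or not confirmed. Report all three counts over the full denominator, with a Clopper-Pearson 95% interval for confirmed passage and best- and worst-case bounds for the not-confirmed group. State in SAP 6.5 that its rule of removing missing values does not apply to transit, so the endpoint is not left without a missing-data rule.

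**Optional and minor.** Keep mITT as primary for sensitivity and specificity. Add one supplementary analysis by EGD class that counts a swallowed capsule with no reading as incorrect, labelled as worst case and as departing from the SAP 5.1 definitions. Give best- and worst-case bounds for subjects with no EGD. For the accuracy endpoints, refer to these instead of relying only on the statement that missing data are random.

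**Cost.** Low: SAP wording and a few extra tables from data already collected, with no change to the primary tests or to any procedure. The figures may look slightly less favourable, and the worst-case bounds are pessimistic by design. If results are already known, the additions must be labelled post hoc.

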## **STATISTICAL ANALYSIS PLAN**

outlier. If data points are identified as outliers sensitivity analysis may be performed to examine the impact of including or excluding the outliers. Any substantive differences in these analyses will be reported. It is assumed that all missing data will be random.

In mITT population, subjects with missing data will not be counted in the percentage. Number of missing values will be reported.

In Safety population, for AEs with a missing start date, the AE will be considered treatment-emergent unless there is additional information indicating that the AE started prior to study treatment and AEs for which the relationship is missing, will be considered related

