## **STATISTICAL ANALYSIS PLAN**

- Total monitoring time
- Device malfunctions (yes/no and type)
- Time between PillSense reading and EGD start time
- PillSense location at time of EGD (stomach or duodenum)
- Other clinically relevant endoscopic findings (yes/no) actual findings will be in listing.
- Additional interventions performed (yes/no) type in listing unless they can be summarized
- Time to PillSense excretion (passage) from the GI tract

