### **8. STATISTICAL METHODOLOGY FOR ENDPOINTS**

#### **8.1. Statistical Methods for the Primary Endpoint**

The estimate of sensitivity will be provided together with an exact (Clopper-Pearson) 95% confidence intervals for the true sensitivity. The null and alternative hypotheses for sensitivity are as follows:

$$H_0: p_1 \leq 0.75$$

vs.

$$H_1: p_1 > 0.75$$

where  $p_1$  denotes the true sensitivity. A one-sided, continuity-corrected z-test will be used to test the null hypothesis at the 0.025 level of significance.

The estimate of specificity will be provided together with an exact (Clopper-Pearson) 95% confidence intervals for the true specificity. The null and alternative hypotheses for specificity are as follows:

$$H_0: p_2 \leq 0.60$$

vs.

$$H_1: p_2 > 0.60$$

where  $p_2$  denotes the true specificity. A one-sided, continuity-corrected z-test will be used to test the null hypothesis at the 0.025 level of significance.

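### Subjects with no capsule reading are left out of both co-primary tests, and no visible analysis shows whether success survives counting them

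*SAP*

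**What the plan says.** SAP 6.4 limits the mITT set to subjects with both PillSense and EGD data and states, in part: "Any patients with missing primary endpoint data (either no PillSense Capsule reading or no EGD result) will be excluded from the primary and secondary endpoint". The same sentence goes on to promise that the frequency of and reasons for such exclusions will be reported. SAP 6.5 adds "It is assumed that all missing data will be random", and says that mITT subjects with missing data are left out of the percentages.

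Other parts of the SAP bear on this:

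- Section 5.1 defines true and false positives and negatives, with no category for an absent reading.
- Section 6.2 counts the specificity enrolment target of 60 in mITT patients, so a non-reading in a subject without a bleed is replaced by further enrolment.
- Section 7.1 plans a flowchart of subjects excluded from mITT, with reasons.
- Section 7.6 lists "Device malfunctions (yes/no and type") among the procedure summaries.
- The only sensitivity analysis in the visible text is an optional one for outliers, in 6.5.

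The first objective, in Protocol 7.3, is "to demonstrate the PillSense System can detect blood in the stomach in clinically relevant scenarios and heterogeneous environment of the upper GI tract".

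**The concern.** In this study the index device can itself produce the missing value. If a swallowed capsule yields no result, the absence of data may be related to how the device performs in the conditions under test. A blanket assumption of randomness is hard to defend for that kind of missingness.

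The EGD result may still be available for such a subject, so the subject can be classified as bleeding or not bleeding. Excluding the subject means that both co-primary estimates answer the question of how accurate the device is when it gives a reading. That is a legitimate quantity, but narrower than performance among all who swallowed a capsule, which is what a reader of the first objective would also want to see. At stake is whether a declared success against the 75% and 60% goals would still stand with non-readings counted. Nothing in the visible plan would tell the reader.

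**Working it through.** **Inputs.** SAP 6.2: "True sensitivity: 0.975"; "Performance Goal: 0.75"; true specificity 0.80 against a goal of 0.60; "One-sided alpha = 0.025" for each endpoint; 86 subjects, 26 with and 60 without UGIB. SAP 8.1: "A one-sided, continuity-corrected z-test will be used to test the null hypothesis at the 0.025 level of significance". The documents give no non-reading rate, so the rate r below is an assumption, shown over a range.

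**Test.** z = (x/n − p0 − 1/(2n)) / √(p0(1 − p0)/n), with success if z ≥ 1.96. The SAP does not state which variance is used. The null variance is taken here because it reproduces the planned power.

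**Reproducing the plan's figure.**

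- Sensitivity, n = 26: 25/26 gives (0.9615 − 0.75 − 0.0192)/0.0849 = 2.26, a pass. 24/26 gives 1.81, a fail. So 25 are needed.
- Specificity, n = 60: 44/60 gives (0.7333 − 0.60 − 0.0083)/0.0632 = 1.98, a pass. 43/60 gives 1.71, a fail. So 44 are needed.
- Exact binomial power: P(X ≥ 25 | 26, 0.975) = 0.863 and P(X ≥ 44 | 60, 0.80) = 0.923. The product is 0.796, which matches the SAP's figure of about 80%. The normal approximation gives 0.901 × 0.905 = 0.815.

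**Can exclusion change a pass or fail?** Take subjects with a known EGD result and count each non-reading as incorrect.

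| Situation | Non-readings excluded | Non-readings counted as incorrect |
|---|---|---|
| 26 bleeders, 2 non-readings | 23/24, z = 2.12, passes | 23/26, z = 1.36, fails |
| 60 non-bleeders, 3 non-readings | 42/57, z = 1.97, passes | 42/60, z = 1.45, fails |
| 27 bleeders, 1 non-reading | 25/26, z = 2.26, passes | 25/27, z = 1.89, fails the planned test |
| 28 bleeders, 2 non-readings | 25/26, z = 2.26, passes | 25/28, z = 1.53, fails |
| 28 bleeders, 2 non-readings | 26/26, z = 2.72, passes | 26/28, z = 1.964, passes |

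The third row depends on the test. An exact binomial test of 25/27 gives one-sided p = 0.021, and the Clopper-Pearson lower limit is 0.757, above the goal. The fourth row fails both tests (exact p = 0.055). The fifth passes both (exact p = 0.017).

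**Effect on the probability of success.** If a fraction r of capsules gives no reading and these count as incorrect, effective sensitivity is 0.975(1 − r). The probability of meeting the goal with 26 bleeders is P(X ≥ 25 | 26, 0.975(1 − r)).

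| Assumed r | Effective sensitivity | Probability of meeting the sensitivity goal |
|---|---|---|
| 0 | 0.975 | 0.863 |
| 0.5% | 0.970 | 0.818 |
| 1% | 0.965 | 0.772 |
| 2% | 0.956 | 0.677 |
| 5% | 0.926 | 0.419 |

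Applying the same r to specificity, as 0.80(1 − r), joint power falls from 0.796 to 0.677 × 0.866 = 0.586 at 2% and 0.419 × 0.742 = 0.311 at 5%.

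**The case against.** Several points on the other side stand.

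- **Disclosure.** A reader might infer that failed readings are hidden. They are not: SAP 6.4, 7.1 and 7.6 provide for frequency, reasons, a flowchart and malfunction types. What is missing is any commitment to classify non-readings by EGD result or to repeat the goal tests.
- **Direction.** A reader might infer that exclusion always biases in the device's favour. That holds only relative to counting a non-reading as incorrect. For accuracy given a reading, which is what section 5.1 defines, the direction is unknown. If readings were lost mainly in easily detected bleeds, the reported sensitivity would be too low.
- **The goals.** It is tempting to say that the 75% and 60% goals were set for all swallowed capsules. Protocol 7.2 derives them from a capsule-endoscopy meta-analysis and does not say how failed examinations were handled there.
- **Cause and frequency.** Listing malfunctions does not show that they are expected or that they lose readings. The exclusion also covers subjects with no EGD, who have no reference result, and Protocol 7.5.4 withdraws those who cannot or will not swallow. Neither group represents a device failure.
- **The SAP 6.5 sentence.** It is general and is not tied to 6.4, so it should not be read as a stated justification for this exclusion.
- **Clinical role.** SAP section 1 presents the device as a supplement to standard care, and all subjects are to receive EGD. A non-reading can fairly be called uninformative rather than a misclassification.

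These points argue for keeping the mITT analysis as primary and for calling the addition a bound. They do not remove the gap, because disclosure leaves both test results unchanged.

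**Conclusion.** The concern holds as a gap in the supportive analyses, not as an error in the primary one. By rule, non-readings with a known EGD result have no influence on either co-primary test, and no visible analysis shows whether success survives counting them. Some SAP text is redacted, including a contents entry between 6.2 and 6.4, so this is a statement about the visible text only.

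The textual gap is certain. Its impact is not: it is zero if every capsule reads, and no rate is given. It could be material because the sensitivity test tolerates one miss in 26, so two non-readings among bleeders or three among non-bleeders can reverse a result at the margin. It need not be: a perfect 26/26, which has probability 0.975^26 = 0.52 under the planning assumption, survives two further non-readings. The success probabilities rest on the assumed rates, on the SAP's planning values and on treating non-readings as incorrect.

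**What to change.** Keep the mITT analysis as primary and make four changes.

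1. In SAP 6.4 and 8.1, prespecify a worst-case supportive analysis of all subjects who swallowed a capsule and have an EGD result. Count a non-reading as an incorrect result: not detected if EGD is positive, not correctly negative if EGD is negative. Label it a bound, and do not relabel these subjects as false positives, because section 5.1 reserves that term for a bleed that the capsule detected.
2. Repeat both goal comparisons on this set and state with any success claim whether it survives.
3. Report the proportion of swallowed capsules with no reading, with an exact 95% confidence interval, by EGD result.
4. In SAP 6.5, state that the random-missingness assumption does not apply to absent PillSense readings.

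The cost is SAP wording and one further two-by-two table from data already collected. The supportive estimates may be slightly less favourable than the primary ones.
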